9.7.2 Follow-Up Evaluations

The number and percentage of subjects who had pregnancy confirmation, return to menses and received a new contraceptive method after discontinuation of study treatment will be summarized. The denominator used for the percentages will be the number of subjects in the Safety Population who discontinued study medication due to a pregnancy wish.

The time from last dose of study medication to return of menses will be summarized using descriptive statistics in the Safety Population.

The following will be summarized using descriptive statistics for subjects in the Safety Population who discontinued study medication due to a pregnancy wish who selected the corresponding fertility information:

- Time from last dose of study medication to estimated date of conception
- Time from last dose of study medication to new contraceptive method

The estimated date of conception is derived as the expected date of pregnancy term – 38 weeks (266 days).

Data for follow-up evaluations will be listed for subjects in the Safety Population who discontinued study medication due to a pregnancy wish.

9.8 Population Pharmacokinetics Analysis

9.8.1 Data Included in Analysis

Data from study MIT-Es0001-C302 are very sparse (two samples at each of two visits per subject, and collected relatively close together). These data alone will likely not support identification of many of the model parameters. To insure identifiability of parameters required to meet the objectives, rich data from study Es0001-C101 will be included in the data set. Additional data from study MIT-Es0001-C103 may be included in the population PK analysis if relevant parameters are not identifiable with data from only MIT-Es0001-C101.

9.8.2 Objectives

The objectives are to assess the effect of various individual characteristics/covariates (e.g., body weight, race, smoking, and fed vs fasted status) on the pharmacokinetics (PK) of 15 mg Estetrol (E4)/3 mg Drospirenone (DRSP). As data permit, PK parameters will include, but are not limited to:

- Primary parameters (i.e. model parameters):
 - Apparent clearance (CL/F).
 - Central volume of distribution (V/F).
 - Lag time of Absorption (Tlag), if necessary.
 - Relative bioavailability for fed vs fasted state.
- Secondary parameters (i.e. derived parameters):
 - Maximum concentration (Cmax).
 - Time to Cmax (Tmax).
 - Extent of exposure for the dosing interval (AUCtau) at steady state.
 - Terminal half-life ($t^{1/2}$).
 - Predicted trough drug concentration (Ctrough) at steady state.
 - Distribution half-life $(t\frac{1}{2})$ (if applicable).

9.8.3 Assumptions

Missing covariates will be imputed as the most recent reported value (last value carried forward) if any are reported for that subject. If no value is available, missing covariates will be imputed as the median of all other subjects within the study.

Patients will record time of the most recent dose prior to sample collection. This dose will be assumed to be at steady state, with a 24-hour dosing interval.

Two separate models will be developed, one for E4 and one for DRSP. It is assumed these drugs do not interact.

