4.3 Predetermined Subgroups

The key subgroup in this study is subjects aged 16 to 35 years, inclusive, at the time of screening. This subgroup is used for the primary efficacy population. All data regarding disposition, baseline characteristics, compliance, exposure and contraceptive efficacy will be presented for subjects aged 16 to 35 years and for all subjects within the specified analysis population.

In addition, subgroup analyses will be performed for the Pearl Index and bleeding data (specifically unscheduled bleeding and spotting and the absence of scheduled bleeding) for the following categories:

- Body Mass Index (BMI) categories (< 30, ≥ 30 kg/m²) at Baseline
- Race category (White, Black or African American, Asian, American Indian or Alaska Native, Native Hawaiian or other Pacific Islander, Other Race)
- Starters (including true new users)/Switchers (see Section 5.5)

- Smokers/Non-smokers at Baseline
- Age (\geq 16 to \leq 25; > 25 to \leq 35 and > 35 years old) at Screening

The non-smokers group includes subjects who are former smokers and never smokers. The smokers group includes subjects who are current smokers. The other race group includes subjects who selected more than one race or whose race was recorded as other race on the CRF.

Quality of life data will be presented for all subjects and for starters and switchers separately.

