9.8.5 Study MIT-Es0001-C302

A Multicenter, Open-label, Single-Arm Study to Evaluate the Contraceptive Efficacy and Safety of a Combined Oral Contraceptive Containing 15 mg Estetrol and 3 mg Drospirenone.

Two PK samples will be taken from the subjects in the Population PK Substudy at Visits 3 and 4. All subjects included in the Substudy will provide a sample for PK analysis at the time they check into the site (PK sampling 1). An additional blood sample (PK sampling 2) will be collected approximately two hours after the first sample.

The following timings will be recorded by the site personnel in the eCRF:

- The exact times of the last study medication dosing and the PK samplings 1 and 2.
- Depending on the time scheduled for the study site visit (Visit 3 & 4), subjects were instructed on when they need to take their medication either as usually done at home or on site. One blood sample will be taken before dosing and the second blood sample will be taken within 2-hour postdose. The subjects were instructed to record the time of the dosing in the Diary.
- The time of the last meal intake before the last study medication dosing before study visit.

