9.8.6 Study Es0001-C101

A study to characterize the effect of food on the bioavailability of 15 mg Estetrol/3 mg Drospirenone tablets in healthy female volunteers.

Es0001-C101 was an open-label, randomized, balanced, single-dose, two-treatment, two-period, twosequence crossover study conducted under medical supervision in 28 healthy female volunteers. All subjects entered the study site at least 12 hours before each dosing and fasted for at least 10 hours prior to each dose. All subjects received the following 2 treatments:

- Treatment A (Reference): a single 15 mg E4/3 mg DRSP tablet without food (fasted).
- Treatment B (Test): a single 15 mg E4/3 mg DRSP tablet with food (fed).

All subjects received both Treatment A and Treatment B either at the first treatment period (Period 1) or the second treatment period (Period 2). Approximately half of the subjects were randomized to receive either Treatment A followed by Treatment B (Sequence AB), or Treatment B followed by Treatment A (Sequence BA) as described in Table 5.

PK Sampling: Blood samples were collected prior to each dose and at 10, 20, 30 and 45 min, and then at 1, 1.25, 1.5, 1.75, 2, 2.5, 3, 4, 6, 8, 12, 16, 24, 36, 48, and 72 hours post-dose for pharmacokinetic (PK) analysis.

Table 5.Treatment Sequences

Sequence	Period 1	Period 2
АВ	Treatment A: 1 tablet 15 mg E4/3 mg DRSP in fasted conditions	Treatment B: 1 tablet 15 mg E4/3 mg DRSP in fed conditions
ВА	Treatment B: 1 tablet 15 mg E4/3 mg DRSP in fed conditions	Treatment A: 1 tablet 15 mg E4/3 mg DRSP in fasted conditions

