9.8.11 PopPK Model Evaluation

A traditional approach to model selection will be used. In this approach, an initial simple model is run. Additional features are sequentially added to this model (e.g., compartments, lag times, variance terms, covariates), testing each addition for statistical significance, improvement of diagnostic graphics and/or biological plausibility. Model features (e.g., lag times, compartments) will be added or removed based on evaluation of diagnostic plots, consideration of biological plausibility, and statistical tests. The goodness-of-fit between hierarchical models is measured by the difference in the objective function value (OFV) produced by NONMEM. The difference in OFV between two hierarchical or nested models is approximately χ^2 distributed, with n degrees of freedom. As such, the OFV is used to obtain the significance level for the difference between two nested models. The criteria for forward addition will be p<0.05 and the criteria for backward elimination will be p<0.001. Covariate analyses will be performed separately for the PK of E4 and DRSP.

Assessment of model adequacy and decisions about increasing model complexity will be driven by the data and guided by goodness-of-fit criteria, including:

1. Visual inspection of diagnostic plots (e.g.,observed vs. predicted concentration, residual/weighted residual versus predicted concentration or time, and histograms of individual random effects).

2. Successful convergence of the minimization routine with at least 2 significant digits in parameter estimates. Successful minimization and covariance steps will be desired, but not required.

- 3. Plausibility of parameter estimates.
- 4. Precision of parameter estimates, if available.
- 5. Correlation between model parameter estimation errors < 0.95.
- 6. Likelihood ratio test.
- 7. Asymptotic and or Bootstrap estimate of confidence interval for parameter estimates.

Covariates to be considered during population pharmacokinetic model building include, but are not limited to, variables such as body weight, race, smoking, and fed vs fasted status. Pre-specified hypotheses will be examined first, followed by hypotheses generated from diagnostic plots. If applicable, this will be followed by an automated covariate search (SCM user guide).

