9.8.11.1 Visual Predictive Check

In order to verify that the final model adequately predicts both the central tendency and the variability of the observed data, a visual predictive check (VPC) stratified by weight, race, smoking status, and fed/fasted status will be performed. VPC plots will be made for two or three strata for weight and each stratum for the categorical covariates. For the VPC, simulations will be performed using the final model and final model parameters. The original data set will be used as a template for simulation input. Simulations will be performed to generate approximately 1,000 simulated observations at each time point; if 1,000 simulated observations are not feasible based on the model run times, a reduced number of simulated observations will be used. A graphical comparison will be made between the observed data and the model predicted median and 95% prediction interval over time. Additional VPC plots may be generated to include confidence intervals for the median and prediction intervals of the simulated data. VPC will be conducted in PsN and the result will be summarized using Xpose (Jonsson and Karlsson, 1999).

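### The single imputation rule for missing popPK covariates can misclassify fed/fasted status, which belongs to one dose, and its median fallback is undefined for race

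*SAP*

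**What the plan says.** SAP 9.8.3 gives a two-tier rule. The first tier is: "Missing covariates will be imputed as the most recent reported value (last value carried forward) if any are reported for that subject". The second applies only when the first cannot: "If no value is available, missing covariates will be imputed as the median of all other subjects within the study". Neither sentence distinguishes types of covariate. The other missing-data paragraph in the popPK section, SAP 9.8.9.1, gives only missing dose times as its example and does not mention covariates.

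SAP 9.8.11 names the covariates as "variables such as body weight, race, smoking, and fed vs fasted status". The SAP itself separates weight from the rest in 9.8.11.1: "VPC plots will be made for two or three strata for weight and each stratum for the categorical covariates".

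Food status in this trial comes from an item recorded for each PK visit (Protocol 9.6.4.2, SAP 9.8.5): "The time of the last meal intake before the last study medication dosing before study visit". In the supporting food-effect study C101 (SAP 9.8.6), each of 28 women was dosed once fed and once fasted.

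SAP 9.8.4 lists ten prespecified hypotheses and reserves formal conclusions for them. Numbers 5 and 10 concern food, 3 and 8 race, 4 and 9 smoking.

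**The concern.** A rule that suits body weight has been written for all covariates. Two mismatches follow.

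First, food status describes the meal before one tablet. Using the Visit 3 value at Visit 4 attaches a Cycle 2 meal to a Cycle 4 dose. The value then enters the model as if observed, and wrong values blur the fed/fasted contrast that hypotheses 5 and 10 test.

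Second, a median needs an ordering. Race has none, so the fallback value can depend on which number the data set assigns to which category.

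At stake are the covariate conclusions of the PK substudy, which is one of the other secondary objectives. The Pearl Index, the sample size and the safety analyses are not touched.

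**Working it through.** The plan states no figure that depends on this rule, so there is nothing to reproduce. The checks below show how often the rule gives a wrong or undefined value when it is used.

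**Inputs from the documents:** about 500 women in the substudy, with PK sampling at Visits 3 and 4; C101 with 28 women, each dosed once fed and once fasted; six race categories in SAP 4.3; two smoking levels.

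**Assumptions, because the documents are silent:** the share p of doses taken fed, the agreement of food status between visits, the race mix, and the amount of missing data.

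**1. Carrying food status forward.** If status at the two visits is independent, the carried value is wrong when one dose is fed and the other fasted:

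error = p(1−p) + (1−p)p = 2p(1−p)

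| p | Carry-forward error, 2p(1−p) | Error if the most frequent status were used, min(p, 1−p) |
|---|---|---|
| 0.1 | 2 × 0.1 × 0.9 = 18% | 10% |
| 0.3 | 2 × 0.3 × 0.7 = 42% | 30% |
| 0.5 | 2 × 0.5 × 0.5 = 50% | 50% |

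These are percentages of imputed visits, not of all visits. If instead a woman's status agrees between visits with probability a, the error is 1 − a: 20% to 30% for an assumed agreement of 70% to 80%.

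**2. What this does to the contrast.** Take the worst case, independence, and let m be the share of this trial's visits whose status was carried forward. Take a simple fed-minus-fasted comparison with true difference D. Among imputed visits the carried label says nothing about the actual dose, so both label groups have the same expected response there. The expected observed difference is (1−m)D + m × 0 = (1−m)D. The dilution is therefore proportional to m, which is not known.

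**3. Food status in C101.** Carry-forward from period 1 to period 2 would be wrong for every woman, because the design switches the status. The median of 28 zeros and 28 ones is 0.5, which is neither category. Both are consequences of the rule as written; status there is assigned by design and should rarely be missing.

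**4. Median race.** I took four assumed mixes of 500 women over six categories and computed the median under all 6! = 720 numeric codings.

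| Largest category | Assumed counts | Median is the largest category | Median is another category | Median falls between two codes |
|---|---|---|---|---|
| 75% | 375, 75, 20, 5, 5, 20 | 100% | 0% | 0% |
| 55% | 275, 150, 40, 5, 5, 25 | 100% | 0% | 0% |
| 48% | 240, 170, 45, 5, 5, 35 | 50% | 40% | 10% |
| 40% | 200, 190, 60, 10, 10, 30 | 33% | 53% | 13% |

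A category above 50% always covers the middle of the sorted list, whatever the coding. Below that threshold the answer depends on the coding.

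**5. Two-level covariates.** The median of a 0/1 variable is its more frequent value, except at an exact tie. For smoking, and for food status within this trial, the fallback is therefore ordinary most-frequent-value imputation.

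**The case against.** The best defence is that the rule will seldom matter. Race and tobacco use are collected at screening (Protocol 9.5.1, 9.6.4.4, 9.6.4.6). C101 supplies rich data with food status fixed by design, and SAP 9.8.1 brings it in precisely because this trial's own samples are sparse. A visit without a usable dose time is already dealt with under 9.8.9.1. What remains is visits with a dose time but no meal time, and nobody can say from the documents how many there will be. Women take the tablet at about the same time each day, so some consistency of food status is plausible. All of this stands, and it limits the size of the problem.

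The defence also disposes of a broader reading. A reader might infer that imputed race, smoking and food values are all arbitrary or wrong, and that every hypothesis on them is compromised. The documents do not support that:

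- The median is a fallback, not a second step applied to every gap.
- Carry-forward is harmless for race, which is fixed.
- For smoking the fallback is the most frequent category, a conventional choice.
- The race median depends on coding only without a majority category. The documents give no race distribution, and SAP 9.8 does not say which grouping the PK model will use. The six categories come from the subgroup list for the Pearl Index and bleeding data; Protocol 12.4.3 has four.
- Nothing says that food status changes with every dose. It can differ between doses, and a given woman may always dose in the same state.

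What the defence does not answer is why a value known to belong to one dose should be assigned to another. Nor does it supply an exception for categorical covariates; there is none in the popPK section.

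**Conclusion.** The point holds in a limited form. For food status, SAP 9.8.3 prescribes a step that can enter wrong values into hypotheses 5 and 10. Under independence between visits the error is 18% to 50% of imputed visits for p from 0.1 to 0.5, and it is lower with within-woman consistency. For race, the fallback is undefined as written and depends on the coding when no category exceeds 50%. For smoking, it amounts to the most frequent value.

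The overall effect scales with a missing-data rate that the documents do not give. It is probably small, especially for race and smoking. No sample size or power figure changes.

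A reader might also infer that missing food status will be systematic, because women who dose in the morning take the tablet on site between the two samples while the listed meal-time item refers to the dose before the visit. The wording allows that reading, but whether the eCRF also records a meal time for the on-site dose cannot be settled from these documents, so the conclusion does not rest on it.

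**What to change.** Amend SAP 9.8.3 as follows:

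- Limit median imputation to continuous covariates such as body weight.
- For missing race or smoking, use the most frequent category, and add a sensitivity run that excludes those women.
- Never carry food status from one dose to another. Either code it as unknown for that dose with its own effect, or drop the affected records from all models being compared. Dropping them only for hypotheses 5 and 10 would not work: SAP 9.8.11 compares nested models by the difference in objective function value, and that requires the same data in both.
- Report the number of imputed values for each covariate.

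The cost is a few sentences in the SAP, one coding rule for the NONMEM data set, one sensitivity run, and either a few lost records or one extra parameter. If very few doses are coded unknown, their effect will be poorly estimated and dropping the records is the simpler choice.

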9.8.4 Prespecified Hypotheses

Pre-specified hypotheses will be tested before any hypotheses that are based on diagnostic plots. Formal conclusions will be drawn only from these prespecified hypotheses. Results of other hypotheses (e.g., those based on diagnostic plots) will be considered exploratory and will not lead to conclusions.

- 1. Effect of body weight on volume of distribution of E4.
- 2. Effect of body weight on clearance of E4
- 3. Effect of race on clearance for E4.
- 4. Effect of smoking status on clearance for E4.

Protocol no: MIT-Es0001-C302

- 5. Effect of fed vs fasted state on rate (e.g. Ka) or extent (e.g., F) of absorption for E4.
- 6. Effect of body weight on volume of distribution of DRSP.
- 7. Effect of body weight on clearance of DRSP
- 8. Effect of race on clearance of DRSP.
- 9. Effect of smoking status on clearance of DRSP.
- 10. Effect of fed vs fasted state on rate (e.g. Ka) or extent (e.g., F) of absorption for DRSP.

9.8.5 Study MIT-Es0001-C302

A Multicenter, Open-label, Single-Arm Study to Evaluate the Contraceptive Efficacy and Safety of a Combined Oral Contraceptive Containing 15 mg Estetrol and 3 mg Drospirenone.

Two PK samples will be taken from the subjects in the Population PK Substudy at Visits 3 and 4. All subjects included in the Substudy will provide a sample for PK analysis at the time they check into the site (PK sampling 1). An additional blood sample (PK sampling 2) will be collected approximately two hours after the first sample.

The following timings will be recorded by the site personnel in the eCRF:

- The exact times of the last study medication dosing and the PK samplings 1 and 2.
- Depending on the time scheduled for the study site visit (Visit 3 & 4), subjects were instructed on when they need to take their medication either as usually done at home or on site. One blood sample will be taken before dosing and the second blood sample will be taken within 2-hour postdose. The subjects were instructed to record the time of the dosing in the Diary.
- The time of the last meal intake before the last study medication dosing before study visit.

9.8.6 Study Es0001-C101

A study to characterize the effect of food on the bioavailability of 15 mg Estetrol/3 mg Drospirenone tablets in healthy female volunteers.

Es0001-C101 was an open-label, randomized, balanced, single-dose, two-treatment, two-period, twosequence crossover study conducted under medical supervision in 28 healthy female volunteers. All subjects entered the study site at least 12 hours before each dosing and fasted for at least 10 hours prior to each dose. All subjects received the following 2 treatments:

- Treatment A (Reference): a single 15 mg E4/3 mg DRSP tablet without food (fasted).
- Treatment B (Test): a single 15 mg E4/3 mg DRSP tablet with food (fed).

All subjects received both Treatment A and Treatment B either at the first treatment period (Period 1) or the second treatment period (Period 2). Approximately half of the subjects were randomized to receive either Treatment A followed by Treatment B (Sequence AB), or Treatment B followed by Treatment A (Sequence BA) as described in Table 5.

PK Sampling: Blood samples were collected prior to each dose and at 10, 20, 30 and 45 min, and then at 1, 1.25, 1.5, 1.75, 2, 2.5, 3, 4, 6, 8, 12, 16, 24, 36, 48, and 72 hours post-dose for pharmacokinetic (PK) analysis.

Table 5.Treatment Sequences

Sequence	Period 1	Period 2
АВ	Treatment A: 1 tablet 15 mg E4/3 mg DRSP in fasted conditions	Treatment B: 1 tablet 15 mg E4/3 mg DRSP in fed conditions
ВА	Treatment B: 1 tablet 15 mg E4/3 mg DRSP in fed conditions	Treatment A: 1 tablet 15 mg E4/3 mg DRSP in fasted conditions

9.8.7 Study MIT-Es0001-C103

A Randomized, Double-Blind, Placebo-Controlled, Parallel, Single Center Study To Investigate The Pharmacokinetics, Safety, Tolerability, And QT Concentration-Effect Modelling Of Estetrol (E4) In Combination With Drospirenone (DRSP) After Single And Multiple Dosing In Healthy Women.

MIT Es0001-C103 was a randomized, double-blind, placebo-controlled, parallel, single and multiple oral dose study to investigate the PK, safety and tolerability of therapeutic and supratherapeutic single and multiple doses of E4 in combination with DRSP in healthy female subjects. A total of 42 healthy female subjects were to be enrolled in 3 groups of 14 subjects each.

Subjects received a single dose on Day 1 and after washout of at least 14 days, multiple doses during 14 consecutive days from Days 15 to 28.

The following treatments in Table 6 were administered:

	Dose Level E4 (mg)	Dose Level DRSP (mg)	Dosage
Group 1	15	3	Therapeutic E4/DRSP dose level
Group 2	30	6	2 times therapeutic E4/DRSP dose level
Group 3	60	12	4 times therapeutic E4/DRSP dose level

Table 6.MIT-ES0001-C103 Treatments

E4 = Estetrol; DRSP = Drospirenone.

Drug administration on Days 1 and 28 were under fasted conditions. Drug administration on Days 15 to 27 were at the same time of day as on Days 1 and 28, without regard to meals; however, subjects will be fasted before all clinical laboratory assessments.

PK sampling: Samples for pharmacokinetic analysis were collected at the following times:

On Day 1 and Day 28: at pre-dose and at 15 and 30 minutes and 1, 1.5, 2, 3, 4, 6, 8, 12, 16, 24, 36, 48, 72, 96, 120, 144, and 168 hours post-dose.

On Days 17, 19, 21, 23, 25 and 27: at pre-dose.

